### **Surgical Resection following Initial Response**

Investigators may choose to resect solitary lesions in participants with residual disease and render the participant free of macroscopic disease. Participants enrolled in this study may have lesions surgically resected only following consultation with the medical monitor and following the Week 24 tumor imaging assessments. If additional tumor shrinkage is noted compared to the tumor imaging assessments at Week 18, it is highly encouraged that surgical resection be delayed until subsequent scans fail to demonstrate further shrinkage. Participants with a confirmed partial response (PR) who go on to have surgical resection of remaining disease will be considered a PR. Participants with stable disease (SD) who go on to have surgical resection of remaining disease will be considered a SD. Participants may continue treatment after surgery. Tumor tissue of any resected solitary lesion should be submitted to BMS (see [Section 5.6.2](#)). Detailed instructions of the obtaining, processing, labeling, handling, storage, and shipment of these specimens will be provided in a separate procedure manual at the time of study initiation.

### **3.5 Discontinuation of Participants following any Treatment with Study Drug**

Participants MUST discontinue investigational product (and non-investigational product at the discretion of the investigator) for any of the following reasons:

- Participant's request to stop study treatment and/or participation in the study
- Any clinical AE, laboratory abnormality, or intercurrent illness which, in the opinion of the investigator, indicates that continued participation in the study is not in the best interest of the participant
- Pregnancy\*
- Termination of the study by BMS
- Loss of ability to freely provide consent through imprisonment or involuntarily incarceration for treatment of either a psychiatric or physical (eg, infectious disease) illness
- Inability to comply with protocol
- Documented disease progression (or documentation of further progression for participants receiving treatment beyond progression; see [Section 4.5.7](#)). Participants without documented disease progression can discontinue study treatment if they have investigator assessed clinical deterioration that is unstable to perform further tumor assessment, and it should be well documented).
- Any AE meeting discontinuation criteria (see [Section 4.5.6](#)).

\* In the case of pregnancy, the investigator must immediately notify the BMS Medical Monitor/designee of this event. In most cases, the study drug will be permanently discontinued in an appropriate manner. If the investigator determines a possible favorable benefit/risk ratio that warrants continuation of study drug, a discussion between the investigator and the BMS Medical Monitor/designee must occur

All participants who discontinue investigational product should comply with protocol specified follow-up procedures as outlined in [Section 5](#). The only exception to this requirement is when a participant withdraws consent for all study procedures including post-treatment study follow-up or loses the ability to consent freely (ie, is imprisoned or involuntarily incarcerated for the treatment of either a psychiatric or physical illness).

If study drug is discontinued prior to the participant's completion of the study, the reason for the discontinuation must be documented in the participant's medical records and entered on the appropriate case report form (CRF) page.

### **3.6 Post Study Drug Follow up**

Participants who discontinue study treatment must continue to be followed for safety up to 100 days following drug discontinuation.

#### **3.6.1 Withdrawal of Consent**

Participants who request to discontinue study drug will remain in the study and must continue to be followed for protocol specified follow-up procedures. The only exception to this is when a participant specifically withdraws consent for any further contact with him/her or persons previously authorized by the participant to provide this information. Participants should notify the investigator of the decision to withdraw consent from future follow-up **in writing**, whenever possible. The withdrawal of consent should be explained in detail in the medical records by the investigator, as to whether the withdrawal is from further treatment with study drug only or also from study procedures and/or post treatment study follow-up, and entered on the appropriate CRF page. In the event that vital status (whether the participant is alive or dead) is being measured, publicly available information should be used to determine vital status only as appropriately directed in accordance with local law.

#### **3.6.2 Lost to Follow-Up**

All reasonable efforts must be made to locate participants to determine and report their ongoing status. This includes follow-up with persons authorized by the participant as noted above. Lost to follow-up is defined by the inability to reach the participant after a minimum of three documented phone calls, faxes, texts, or emails as well as lack of response by participant to one registered mail letter. All attempts should be documented in the participant's medical records. If it is determined that the participant has died, the site will use permissible local methods to obtain the date and cause of death.

If investigator's use of third-party representative to assist in the follow-up portion of the study has been included in the participant's informed consent, then the investigator may use a sponsor-retained third-party representative to assist site staff with obtaining participant's contact information or other public vital status data necessary to complete the follow-up portion of the study. The site staff and representative will consult publicly available sources, such as public health registries and databases, in order to obtain updated contact information. If after all attempts, the participant remains lost to follow-up, then the last known alive date as determined by the investigator should be reported and documented in the participant's medical records.

## **4 STUDY DRUG**

Study drug includes both investigational [medicinal] product (IP/IMP) and non-investigational [medicinal] product (Non-IP/Non-IMP) and can consist of the following:

- All products, active or placebo, being tested or used as a comparator in a clinical trial.
- Study required premedication,
- Other drugs administered as part of the study that are critical to claims of efficacy (eg, background therapy, rescue medications)
- Diagnostic agents: (such as glucose for glucose challenge) given as part of the protocol requirements must also be included in the dosing data collection.

Product description and storage information is described in [Table 4-1](#).

**Table 4-1: Study Drugs for CA209672 - Treatment Period**

Product Description Class and Dosage Form	Potency	Primary Packaging (Volume)/Label Type	Secondary Packaging (Qty)/Label Type	Packaging/Appearance	Storage Conditions (per label)
Nivolumab (BMS-936558-01) Solution for Injection	100 mg (10 mg/mL)	10 mL vial/ Open-label	5 vials per carton/ Open-label	Clear to opalescent colorless to pale yellow liquid. May contain particles	Store at 2 to 8°C. Protect from light and freezing
Ipilimumab Solution for Injection	200 mg (5 mg/mL) 50 mg (5 mg/mL)	40 mL vial 10 mL vial/ Open-label	4 vials per carton 1 vial per carton / Open-label	Clear to opalescent colorless to pale yellow liquid. May contain particles	Store at 2 to 8°C. Protect from light and freezing

#### **4.1        Investigational Product**

An investigational product, also known as investigational medicinal product in some regions, is defined as a pharmaceutical form of an active substance or placebo being tested or used as a reference in a clinical study, including products already with a marketing authorization but used or assembled (formulated or packaged) differently than the authorized form, or used for an unauthorized indication, or when used to gain further information about the authorized form.

The investigational product should be stored in a secure area according to local regulations. It is the responsibility of the investigator to ensure that investigational product is only dispensed to study participants. The investigational product must be dispensed only from official study sites by authorized personnel according to local regulations.

#### **4.2        Non-investigational Product**

Other medications used as support or escape medication for preventative, diagnostic, or therapeutic reasons, as components of the standard of care for a given diagnosis, may be considered as non-investigational products.

#### **4.3        Storage and Dispensing**

The product storage manager should ensure that the study drug is stored in accordance with the environmental conditions (temperature, light, and humidity) as determined by BMS. If concerns regarding the quality or appearance of the study drug arise, the study drug should not be dispensed and contact BMS immediately.

Study drug not supplied by BMS will be stored in accordance with the package insert.

Investigational product documentation (whether supplied by BMS or not) must be maintained that includes all processes required to ensure drug is accurately administered. This includes documentation of drug storage, administration and, as applicable, storage temperatures, reconstitution, and use of required processes (eg, required diluents, administration sets).

For nivolumab and ipilimumab, please refer to the current version of the IBs and/or pharmacy reference sheets for complete storage, handling, dispensing, and infusion information.

Nivolumab is to be administered as an approximately 30-minute IV infusion. At the end of the infusion, flush the line with a sufficient quantity of normal saline or dextrose solution. Ipilimumab is to be administered as an approximately 30-minute IV infusion. At the end of the infusion, flush the line with a sufficient quantity of normal saline or 5% dextrose solution. When both study drugs are to be administered on the same day, separate infusion bags and filters must be used for each infusion. Nivolumab is to be administered first. The nivolumab infusion must be promptly followed by a saline flush to clear the line of nivolumab before starting the infusion. The second infusion will always be ipilimumab and will start at least 30 minutes after completion of the nivolumab infusion, filters changed, and patient observed to ensure no infusion reaction has occurred. Begin study treatment within 3 calendar days of treatment assignment.

#### **4.4 Method of Assigning Participant Identification**

CA209672 is an open-label, non-randomized, parallel-arm study. During the screening visit, the investigative site will call into the enrollment option of the Interactive Voice Response System (IVRS) designated by BMS for assignment of a 5-digit participant number that will be unique. Enrolled participants, including those not dosed, will be assigned sequential participant numbers starting with [REDACTED]. The patient identification number (PID) will ultimately be comprised of the site number and participant number. Those enrolled participants meeting inclusion and exclusion criteria will be eligible to be dosed. Specific instructions and procedures for using IVRS will be provided to the investigational site in a separate document/ manual.

#### **4.5 Selection and Timing of Dose for Each Participant**

##### **4.5.1 Dose Limiting Toxicities**

Dose limiting toxicities are defined as any of the items listed below which occur during the first 6 weeks.

- Any Grade 2 drug-related uveitis or eye pain that does not respond to topical therapy and does not improve to Grade 1 severity within the re-treatment period OR requires systemic treatment
- Any Grade 2 drug-related pneumonitis or interstitial lung disease that does not resolve to dose delay and systemic steroids.
- Any Grade 3 non-skin drug-related adverse event regardless of duration with the exception of laboratory abnormalities
- Any Grade 4 drug-related adverse event including laboratory abnormalities except Grade 4 leukopenia or neutropenia lasting < 7 days
- Any of the following drug-related hepatic function laboratory abnormalities:
  - Grade  $\geq$  3 drug-related AST, ALT or Total bilirubin
  - Concurrent AST or ALT  $>$  3 x ULN and total bilirubin  $>$  2x ULN
  - Grade 3 thrombocytopenia associated with bleeding

##### **4.5.2 Dose Adjustment**

Dosing calculations should be based on the body weight assessed at baseline. If the participant's weight on the day of dosing differs by  $>$  10% from the weight used to calculate the prior dose, the dose must be recalculated. All doses should be rounded to the nearest milligram. There will be no other dose modifications allowed.

##### **4.5.3 Dose Delay Criteria**

Study treatment should be delayed for the following:

- Any Grade  $\geq$  2 non-skin, drug-related AE, except for fatigue
- Grade 2 drug-related creatinine, AST, ALT, and/or Total Bilirubin Abnormalities, with the following exceptions:

- If a participant has baseline AST, ALT, or total bilirubin within the Grade 1 toxicity range, delay dosing for drug-related Grade  $\geq 3$  toxicity
- See [Section 4.5.6](#) for discontinuation criteria for drug-related ALT, AST and/or Total Bilirubin Abnormalities
- Any Grade  $\geq 3$  skin drug-related AE
- Any Grade 3 drug-related laboratory abnormality with the following exceptions:
  - Grade 3 lymphopenia or asymptomatic amylase or lipase does not require a dose delay
- Any AE, laboratory abnormality or inter-current illness which, in the judgment of the investigator, warrants delaying the dose of study medication.

Dosing of nivolumab and ipilimumab should be delayed for any adverse event, laboratory abnormality, or intercurrent illness which, in the judgment of the investigator, warrants delaying the dose of study medication. Study therapy should also be delayed in cases of confirmed or suspected severe acute respiratory syndrome coronavirus 2 (SARS-CoV-2) infection regardless of the severity.

Participants receiving nivolumab in combination with ipilimumab who have drug-related toxicities that meet the criteria for dose delay should have both drugs (nivolumab and ipilimumab) delayed until treatment resumption criteria are met.

Participants who require delay of nivolumab and/or ipilimumab should be re-evaluated weekly or more frequently if clinically indicated and resume nivolumab and/or ipilimumab dosing when retreatment criteria are met.

Dose delay criteria apply for all drug-related adverse events regardless of whether the event is attributed to nivolumab or ipilimumab or both.

Doses of nivolumab or ipilimumab may be interrupted, delayed, or discontinued depending on how well the participant tolerates the treatment. Dosing visits are not skipped, only delayed.

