### **Safety of Nivolumab and Ipilimumab Combination in MSI-H/dMMR Metastatic Colon Cancer**

Study CA209142 is a multi-arm, Phase 2, clinical trial of nivolumab or nivolumab combinations, in recurrent and metastatic MSI-H and non-MSI-H colon cancer.

In the nivolumab + ipilimumab (N+I) cohort, 119 pre-treated MSI-H/dMMR CRC subjects were treated with nivolumab in combination with ipilimumab, as well as a subset of 82 subjects who had received prior 5-fluoropyrimidine, oxaliplatin, and irinotecan (5FU-Oxa-Iri): nivolumab administered intravenously (IV) over 60 minutes at 3 mg/kg combined with ipilimumab administered IV over 90 minutes at 1 mg/kg every 3 weeks for four doses followed by nivolumab administered IV over 60 minutes at 3 mg/kg every 2 weeks until progression.

The overall safety profile of nivolumab in combination with ipilimumab was acceptable in subjects with recurrent or metastatic MSI-H/dMMR CRC who had progression during or after, or have been intolerant to  $\geq 1$  line of treatment(s) for their metastatic disease. No new safety concerns with

combination treatment were identified. As of DBL of 19-Feb-2019 (hereafter, the Feb-2019 DBL) with a clinical data cutoff date of 07-Jan-2019, and a minimum follow-up of 27.5 months for subjects treated with nivolumab + ipilimumab in CA209142, 33 deaths were reported, all of which were due to disease progression and there were no deaths attributed to study drug toxicity. The frequencies of drug-related SAEs were 22.7% for any-grade and 20.2% for Grade 3-4, the frequencies of drug-related AEs leading to discontinuation were 13.4% for any-grade and 10.1% for Grade 3-4. Drug-related AEs of any grade occurred in 95 of 119 evaluable patients (79.8%). Grade 3/4 AEs were reported in 31.9% of subjects. The most common drug-related AEs occurring in  $\geq$  15% of subjects were diarrhea (25.2%), pruritus (20.2%), fatigue (18.5%), hypothyroidism (17.6%), AST increased (16%), pyrexia (15.1%), and rash (15.1%). A similar safety profile was observed between the all-combination treated subjects and the subset of subjects treated with prior 5FU-Oxa-Iri.

Most select AEs and immune-mediated AEs were Grade 1/2. The majority of select AEs and immune-mediated AEs resolved and were manageable using the recommended treatment guidelines for early work-up and intervention.

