### **3.1.4    *Intra-Subject Dose Reductions***

Intra-subject dose reduction is not permitted for any reason. Dose delays for the management of study treatment-related AEs are described in [Section 4.5.3](#).

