### **Arm A:**

- Nivolumab may be delayed until the next planned ipilimumab dose if the next ipilimumab dose is scheduled within the next 12 days. This will permit periodic ipilimumab dosing to be synchronized with nivolumab dosing.
- Ipilimumab should be dosed at the specified interval regardless of any delays in intervening nivolumab doses. However, in order to maintain periodic synchronized dosing of ipilimumab and nivolumab, the dosing days of nivolumab and ipilimumab may be adjusted within the permitted  $\pm 2$  day window, as long as consecutive nivolumab doses are given at least 12 days

apart. Ipilimumab may be delayed beyond the 2-day window if needed to synchronize with the next nivolumab dose.

- If an ipilimumab dose is delayed beyond 6 weeks from the prior ipilimumab dose, then subsequent ipilimumab doses should be rescheduled to maintain the 6-week interval between consecutive ipilimumab doses.
- A dose delay of ipilimumab which results in no ipilimumab dosing for > 12 weeks requires ipilimumab discontinuation, with exceptions as noted in Section 4.5.5.

Arm B, C and D: Participants may be dosed no less than 12 days and 19 days from the previous treatment during Q2W (nivolumab) and Q3W (nivolumab combined with ipilimumab) dosing, respectively.

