#### **4.5.5 Criteria to Resume Treatment**

Participants may resume study treatment when the drug-related AE(s) resolve(s) to Grade  $\leq$  1 or baseline, with the following exceptions:

- Participants may resume treatment in the presence of Grade 2 fatigue.
- Participants who have not experienced a Grade 3 drug-related skin AE may resume treatment in the presence of Grade 2 skin toxicity.
- For participants with Grade 2 AST, ALT and/or Total Bilirubin Abnormalities, dosing may resume when laboratory values return to baseline and management with corticosteroids, if needed, is complete. Participants with baseline Grade 1 AST/ALT or total bilirubin elevations who require dose delays for reasons other than a 2-grade shift in AST/ALT or total bilirubin may resume treatment in the presence of Grade 2 AST/ALT OR total bilirubin.
- Participants with isolated AST/ALT elevations or combined with total bilirubin elevations meeting discontinuation parameters ([Section 4.5.6](#)) should have treatment permanently discontinued, except situations outlined in the [Section 4.5.6](#).
- Drug-related pulmonary toxicity, diarrhea, or colitis must have resolved to baseline before treatment is resumed. Participants with persistent Grade 1 pneumonitis after completion of a steroid taper over at least 1 month may be eligible for retreatment if discussed with and approved by the BMS Medical Monitor.
- Drug-related endocrinopathies adequately controlled with only physiologic hormone replacement may resume treatment after consultation with the BMS Medical Monitor. If participant experienced Grade 3 adrenal insufficiency study treatment should not be resumed regardless of control with hormone replacement.

Participants with SARS-CoV-2 infection (either confirmed or suspected) may resume treatment after all of the following conditions are met:

- At least 10 days (20 days for severe/critical illness) have passed since symptoms first appeared or positive test result (eg, reverse transcription polymerase chain reaction or viral antigen)
- Resolution of acute symptoms (including at least 24 hours has passed since last fever without fever reducing medications)
- Evaluation by the investigator with confirmation that there are no sequelae that would place the participant at a higher risk of receiving investigational treatment.

For suspected cases, treatment may also resume if SARS-CoV-2 infection is ruled out and other criteria to resume treatment are met.

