#### **4.5.6 Treatment Discontinuation Criteria**

Treatment should be permanently discontinued for any of the following:

- Any Grade 2 drug-related uveitis or eye pain or blurred vision that does not respond to topical therapy and does not improve to Grade 1 severity within the re-treatment period OR requires systemic treatment
- Any Grade 3 non-skin, drug-related AE lasting > 7 days, with the following exceptions for drug-related uveitis, pneumonitis, bronchospasm, hypersensitivity reactions, infusion reactions, endocrinopathies, diarrhea, colitis, neurologic toxicity and laboratory abnormalities:
  - Grade 3 drug-related uveitis, pneumonitis, bronchospasm, diarrhea, colitis, myocarditis, neurologic toxicity, hypersensitivity reaction, or infusion reaction of any duration requires discontinuation. Grade 3 drug-related endocrinopathies adequately controlled with only physiologic hormone replacement do not require discontinuation. Grade 3 adrenal insufficiency requires discontinuation regardless of control with hormone replacement.
    - ◆ Grade 3 drug-related laboratory abnormalities do not require treatment discontinuation except:
      - Grade 3 drug-related thrombocytopenia > 7 days or associated with bleeding requires discontinuation.
      - Grade  $\geq 3$  drug-related AST, ALT or Total Bilirubin requires discontinuation\*
      - Concurrent AST or ALT  $> 3 \times$  ULN and total bilirubin  $> 2 \times$  ULN\*
  - \*In most cases of Grade 3 AST or ALT elevation, study drug(s) will be permanently discontinued. If the investigator determines a possible favorable benefit/risk ratio that warrants continuation of study drug(s), a discussion between the investigator and the BMS Medical Monitor/designee must occur.

- Any Grade 4 drug-related adverse event or laboratory abnormality, except for the following events, which do not require discontinuation:
  - Grade 4 neutropenia  $\leq$  7 days
  - Grade 4 lymphopenia or leukopenia
  - Isolated Grade 4 amylase or lipase abnormalities that are not associated with symptoms or clinical manifestations of pancreatitis. The BMS Medical Monitor should be consulted for Grade 4 amylase or lipase abnormalities
  - Isolated Grade 4 electrolyte imbalances/abnormalities that are not associated with clinical sequelae and are corrected with supplementation/appropriate management within 72 hours of their onset

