  - Grade 4 drug-related endocrinopathy adverse events such as hyper- or hypothyroidism, or glucose intolerance, which resolve or are adequately controlled with physiologic hormone replacement (corticosteroids, thyroid hormones) or glucose controlling agents, respectively, may not require discontinuation after discussion with and approval from the BMS Medical Monitor
- Dosing delays lasting  $>$  6 weeks for Q2W dosing (nivolumab monotherapy) or  $>$  8 weeks for Q3W dosing (nivolumab combined with ipilimumab) from the previous dose requires discontinuation. The following exceptions apply:
  - Dosing delays to allow for prolonged steroid tapers to manage drug-related adverse events are allowed.
  - Dosing delays lasting  $>$  6 weeks from the previous dose that occur for non-drug-related reasons may be allowed if approved by the BMS medical monitor.
- Any adverse event, laboratory abnormality, or intercurrent illness which, in the judgment of the Investigator, presents a substantial clinical risk to the participant with continued nivolumab dosing.

Prior to re-initiating treatment in a participant with a dosing delay lasting  $>$  6 weeks, the BMS medical monitor must be consulted. Tumor assessments should continue as per protocol even if dosing is delayed. Periodic study visits to assess safety and laboratory studies should also continue every 6 weeks or more frequently if clinically indicated during such dosing delays.

The assessment for discontinuation of ipilimumab should be made separately from the assessment made for discontinuation of nivolumab. Although there is an overlap among the discontinuation criteria, if discontinuation criteria are met for ipilimumab but not for nivolumab, treatment with nivolumab may continue if ipilimumab is discontinued.

If a participant meets the criteria for discontinuation of ipilimumab but not nivolumab, treatment with nivolumab may not resume until the AE/SAE has fully resolved and the participant has discontinued steroids, if they were required for treatment of the AE/SAE. The relationship to ipilimumab should be well documented in the source documents. Nivolumab should be resumed at the dose according to the treatment schedule ([Table 5.1-2](#), [Table 5.1-3](#) and [Table 5.1-4](#)).

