## **5.3     Safety Assessments**

At baseline, a medical history will be obtained to capture relevant underlying conditions. Baseline signs and symptoms are those that are assessed within 2 weeks prior to dosing. The baseline physical examination should include weight, height, BP, HR, and temperature. These should be performed within 28 days of treatment. Concomitant medications will be collected from within 2 weeks prior to treatment assignment through the study treatment period.

Testing for asymptomatic SARS-CoV-2 infection, for example by reverse transcription polymerase chain reaction (RT-PCR) or viral antigen, is not required. However, some participants may develop suspected or confirmed symptomatic SARS-CoV-2 infection or be discovered to

have asymptomatic SARS-CoV-2 infection during the screening period. In such cases, participants may be eligible for the study after recovery from infection or completion of quarantine period in case of asymptomatic infection/potential exposure.

Toxicity assessments will be continuous during the treatment phase until 100 days (equal to approximately 5 half-lives of nivolumab) after the last dose of nivolumab.

Adverse events and laboratory values will be graded according to the NCI CTCAE version 4.0.

Vital signs should be taken as per institutional standard of care at visits and prior to, during, and after the infusion with nivolumab. The start and stop time of the study drug infusion should be documented. If there are any new or worsening clinically significant changes since the last exam, report these changes on the appropriate AE or SAE page.

Perform additional measures, including non-study required laboratory tests, as clinically indicated or to comply with local regulations. Laboratory toxicities (eg, suspected drug induced liver enzyme evaluations) will be monitored during the follow-up phase via on-site/local labs until all study drug-related toxicities resolve, return to baseline, or are deemed irreversible.

Evaluate participant immediately to rule out cardiac or pulmonary toxicity if participant shows cardiac or pulmonary-related signs (hypoxia, abnormal heart rate, or changes from baseline) or symptoms (eg, dyspnea, cough, chest pain, fatigue, palpitations).

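### The dose-delay rule in Section 4.5.3 exempts fatigue at any grade, so isolated Grade 3 drug-related fatigue of 7 days or less has no mandatory hold, although Section 4.5.5 tolerates fatigue only to Grade 2

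*Combined protocol and SAP*

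**What the plan says.** Four sections of the protocol decide what happens when a participant has drug-related fatigue on a dosing day.

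- **Delay (4.5.3).** The first bullet delays treatment at Grade 2 or higher for any "non-skin, drug-related AE, except for fatigue". The exception names no grade. The other grade-based bullets cover creatinine and liver values, skin events, and laboratory abnormalities. The last bullet leaves any other event to the investigator's judgment.
- **Resumption (4.5.5).** The general threshold is Grade 1 or lower, or baseline. Fatigue gets its own allowance: "Participants may resume treatment in the presence of Grade 2 fatigue".
- **Permanent stop (4.5.6).** Treatment ends for "Any Grade 3 non-skin, drug-related AE lasting > 7 days". Fatigue is not among the Grade 3 events that require a stop at any duration. Grade 4 drug-related events also end treatment, and fatigue is not among the listed Grade 4 exceptions. A separate bullet covers any event that, "in the judgment of the Investigator, presents a substantial clinical risk to the participant" if nivolumab continues.
- **Dose-limiting toxicity (4.5.1).** In the first 6 weeks, a Grade 3 drug-related event that is neither a skin event nor a laboratory abnormality counts as dose-limiting however short it is.

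Section 3.1.4 adds that "Intra-subject dose reduction is not permitted for any reason", so any dose that is given is a full dose.

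**The concern.** The delay rule and the resumption rule do not meet. A participant already on hold may not restart with Grade 3 fatigue unless that was the baseline level. A participant who is not on hold may be dosed with the same event, because the delay rule passes over fatigue at every grade. The protocol's other rules treat short Grade 3 fatigue as serious: it is dose-limiting early in treatment, and it ends treatment once it passes 7 days.

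At stake is whether a full dose goes to someone with a current Grade 3 drug-related toxicity on discretion alone, where most comparable toxicities would trigger a hold by grade. This is a question of participant safety. It does not bear on any estimate.

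**Working it through.** There is no stated figure to reproduce and no calculation to run. The check takes drug-related fatigue at each grade and duration through the rules.

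| Fatigue on the dosing day | Delay required by grade (4.5.3)? | Permanent stop required (4.5.6)? | If already held, may dosing resume (4.5.5)? |
|---|---|---|---|
| Grade 2 | No | No | Yes |
| Grade 3, 7 days or less | No | No | No, unless baseline |
| Grade 3, more than 7 days | No | Yes | Not applicable |
| Grade 4 | No | Yes | Not applicable |

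The Grade 2 row is consistent across sections. In the last two rows the stop rule makes the missing delay irrelevant. Only the second row has neither a required delay nor a required stop.

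Three further steps:

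1. **Can this case arise on a dosing day?** Yes. Any onset in the week before a scheduled dose falls in the window, whatever the dosing interval.
2. **Does the 7-day rule protect in advance?** No. On day 3, for example, nobody knows whether the event will pass 7 days. A full dose can be given, and the same event can become a mandatory stop a few days later.
3. **Does another section impose a hold?** Section 5.3 calls for immediate evaluation for cardiac or pulmonary toxicity and lists fatigue among the relevant "symptoms (eg, dyspnea, cough, chest pain, fatigue, palpitations". That is a work-up rule and does not hold the dose. The management algorithms listed in Section 4.5.8 include none for fatigue. If the fatigue accompanies another drug-related, non-skin event of Grade 2 or higher, that event triggers the delay. The gap is therefore confined to isolated fatigue.

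**Who could still be affected.** By Section 3.1.1 all 36 participants had been treated by 20-Dec-2021, so the latest 6-week dose-limiting window ended by 31-Jan-2022 (20-Dec-2021 plus 42 days). Section 4.5.1 therefore matters here as evidence of how the protocol regards the event. The latest possible 24-month limit is 20-Dec-2023, which is 485 days after Amendment 07 of 22-Aug-2022; late responders may be treated longer. The documents do not say how many participants were still on treatment.

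**The case against.** **The mismatch may be deliberate.** The protocol separates delay and resumption rules elsewhere. Grade 3 lymphopenia and asymptomatic Grade 3 amylase or lipase need no delay, yet Section 4.5.5 has no matching allowance. Grade 2 skin toxicity triggers no delay, but it blocks resumption after a Grade 3 skin event. It follows that a stricter threshold for resuming does not by itself prove an error, and the documents do not state the intent behind the fatigue wording. The comparisons do not explain an exception without a cap, however. The lymphopenia and enzyme exemptions name Grade 3, and Section 4.5.6 goes on to exempt Grade 4 lymphopenia and isolated, symptom-free Grade 4 amylase or lipase from the stop rule, so those rules follow one line. Skin events do trigger a delay from Grade 3. Fatigue has neither feature.

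**Clinical judgment covers the case.** Section 4.5.3 states the judgment-based delay twice. Section 3.5 requires discontinuation when the investigator thinks continuing is not in the participant's interest. Performance status and laboratory tests are scheduled at dosing visits, and thyroid tests on the first day of each cycle. Many investigators would hold the dose anyway. All of this stands and makes the practical effect small. It does not close the gap, because no grade of fatigue triggers any of these provisions.

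**Stronger readings that a reader might infer.** One is that severe fatigue in general escapes the safety rules. It does not: Grade 4, and Grade 3 beyond 7 days, are mandatory stops. Another is a count of affected participants. Section 1.4.4.4 reports drug-related fatigue in 18.5% of 119 patients in Study CA209142, and 9 × 0.185 = 1.67 might be read as a ceiling for Arm D. It is an expected count of fatigue at any grade. The source cohort received 3 mg/kg maintenance with 60- and 90-minute infusions, whereas Arm D receives 240 mg maintenance with 30-minute infusions. No Grade 3 fatigue rate is given for either.

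**Conclusion.** The point holds in a narrow form. As written, the protocol requires no hold for isolated Grade 3 drug-related fatigue that has lasted 7 days or less on a dosing day, while its own resumption rule stops at Grade 2. The conclusion rests on reading the fatigue exception literally and on reading the 7-day limit as time spent at Grade 3.

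The frequency is unknown and likely small. A demonstrated safety failure should not be inferred, because the documents report no case and discretion remains available. No endpoint, population or statistical result changes. This is a cheap improvement with a minor safety benefit.

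**What to change.** In the first bullet of Section 4.5.3, insert *Grade 2* before the word fatigue, so that the exception covers Grade 2 fatigue only. Grade 3 fatigue then requires a delay from onset, and treatment resumes under Section 4.5.5 once it is Grade 2 or lower (or at baseline). Sections 4.5.5 and 4.5.6 need no change.

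Make the change in the next amendment. Section 9.1.1 mentions administrative letters, but a new mandatory hold alters a treatment rule, and that section requires IRB/IEC approval of an amendment before a change is implemented, except for an immediate hazard.

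The cost is an occasional short dose delay. It should rarely run much beyond a week: the fatigue either falls to Grade 2 within 7 days or passes 7 days and meets the existing stop rule, and Section 4.5.3 already asks for re-evaluation at least weekly. No new data, visits or analyses are needed.
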